# Handling of adverse events when date and time of first OLE investigational medicinal product administration is missing

When the date and time of the first OLE IMP administration is missing, all AEs that occurred on or after the day of visit 1 will be considered as TEAEs.

When the time of the first OLE IMP administration is missing, all AEs that occurred on the day of the OLE IMP administration will be considered as treatment-emergent AEs.

# Handling of missing assessment of relationship of adverse events to investigational medicinal product

If the assessment of the relationship to IMP is missing, then the relationship to IMP has to be assumed as possibly related in the frequency tables, but no imputation should be done at the data level.

# Handling of potentially clinically significant abnormalities

If a patient has a missing baseline value he will be grouped in the category "normal/missing at baseline."

For PCSAs with 2 conditions, one based on a change from baseline value and the other on a threshold value or a normal range, with the first condition being missing, the PCSA will be based only on the second condition.

For a PCSA defined on a threshold and/or a normal range, this PCSA will be derived using this threshold if the normal range is missing; eg, for eosinophils the PCSA is >0.5 GIGA/L or >ULN if ULN  $\ge 0.5$  GIGA/L. When ULN is missing, the value 0.5 should be used.

Measurements flagged as invalid by the laboratory will not be summarized or taken into account in the computation of PCSA values.

# 2.5.4 Windows for time points

Data analyzed by time point (including efficacy, laboratory safety data, vital signs, quality of life, ADA) will be summarized using the analysis windows given in Table 1. These analysis windows will be applicable for all analyses, and they are defined to provide more homogeneous data for time point-specific analyses.

Table 1 - Analysis windows definition

Time point	Targeted study day	Analysis window in study days from OLE entry
Week 4	29	15 to 42
Week 8	57	43 to 70
Week 12	85	71 to minimum (98, study day corresponding to first the injection with IMP from kit allocated at Week 12 re-supply IVRS contact)
Week 24	169	155 to 182
Week 36	253	239 to 266
Week 48	337	316 to 357
Week 60	421	400 to 441
Week 72	505	484 to 525
Week 84	589	568 to 609
WeeK 96	673	652 to 693
Week 108	757	729 to 784
Week 120	841	813 to 868
Week 132	924	896 to 951
Week 144	1008	980 to 1035

Time point	Targeted study day	Analysis window in study days from OLE entry
Week 156	1092	1064 to 1119
Week 168	1176	1148 to 1203

Study days are calculated from the day of first OLE IMP injection, the day of first OLE IMP injection being Day 1. For enrolled but not treated patients, Day 1 is the day of visit 1.

.

If multiple valid values of a variable exist within an analysis window, the nearest from the targeted study day will be selected. If the difference is a tie, the value after the targeted study day will be used. If multiple valid values of a variable exist within a same day, then the first value of the day will be selected when time is available, else the scheduled visit will be selected.

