6.2 DURATION OF STUDY PARTICIPATION

6.2.1 Duration of study participation for each patient

The OLE study is planned to be completed in second quarter 2017 which corresponds to a study duration of approximately 168 weeks for the first patients enrolled or until the drug is commercially available for the patient in the respective country, whatever comes first. For patients in the UK, the study will last a maximum of 176 weeks.

The study duration includes up to approximately 3.5 years of treatment for the first patients enrolled, and 10 weeks of follow up after the last IMP injection for all the patients, those who will complete the study and those who will early discontinue whatever the reason.

The study will be considered as completed for a patient in the following situations:

- When the alirocumab is commercially available in the patient's country
- In second quarter 2017, if alirocumab is not yet commercially available in the patient's country

An EOT visit will be done 2 weeks after the last IMP injection and a safety follow up call 10 weeks after the last IMP injection.

The following situations will be considered as premature discontinuation of the patient from the study:

- Any withdrawal from the study to switch to an anti-PCSK9 inhibitor different from commercial alirocumab
- Any other reason

An unscheduled visit should take place within 5 days after the last IMP administration if possible, with assessments normally planned at the EOT visit, and a safety follow up call performed 10 weeks after the last IMP injection (see section 10.3.4).

The end of study per patient is the last protocol planned call. Patients with a Serious Adverse Events (SAEs) or an Adverse Event of Special Interest (AESI) should be followed until resolution, stabilization, or death.

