9.3.1.3 Bioanalytical method

9.3.2 EQ-5D patient questionnaire

EQ-5DTM (13) is a standardized and generic instrument for measuring patient's health status and health-related quality of life (HRQoL) for clinical and economic assessments (See Appendix E).

EQ-5DTM instrument includes 5 items corresponding to the following domains: mobility, self-care, usual activities, pain/discomfort, and anxiety/depression.

Each item can take one of three responses: (1) "no problems", (2) "some problems", and (3) "severe problems".

Response to items can be converted to a standard utility score ranging between -0.594 representing "severe problems" and 1 representing "no problem".

EQ-5D endpoints include:

- Change in proportion of patients within each domain and response categories from baseline to Weeks 12, 24, 48, and End of OLETP.
- Change in mean EQ-5D utility scores from baseline to Weeks 12, 24, 48, and End of OLETP.

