10.1.1.17 End-of-treatment visit: Visit 17/ Week 168/ Month 40 (Day 1177± 7)

The end of study is scheduled to be in second quarter 2017 or when the drug will become commercially available for the patient in the respective country whatever comes first. Thus, the End-of-treatment visit might be performed earlier than on Week 168 according to the date of inclusion of each patient in the OLE study, or if the patient early discontinues the study.

- Collect adverse events
- Record concomitant medication
- Take vital signs including heart rate and blood pressure
- Get body weight measurement
- Physical examination
- Review patient's diet. Patient should be on a NCEP-ATPIII TLC diet or equivalent.
- Data collection on IMP administration and IMP compliance check by review of diary and treatment kit
- IVRS/IWRS contact to document the end of treatment
- Obtain fasting blood sample for:
 - Lipids: measure and/or calculation of total-C, LDL-C, HDL-C, TG, non-HDL-C, Apo B, Apo A-1, ratio Apo B/Apo A-1, and Lp (a)

- Hematology
- Chemistry
- CPK
- Liver panel
- Anti-alirocumab antibodies

- Local urine pregnancy test (females of childbearing potential only).
- Completion of EQ-5D questionnaire by patient.
- Reminders
 - For all the patients, those who prematurely discontinue the treatment irrespective of the reason and those who will complete the study, an appointment will be given for the Follow up call. This phone call will have to be scheduled 10 weeks after last injection (+/- 7 days).

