10.3.4 Handling of patients after permanent treatment discontinuation

Patients who prematurely discontinue study treatment (regardless of the reason) should undergo an unscheduled visit with assessments normally planned at the end of treatment visit (it should take place within 5 days of treatment discontinuation, if possible).

The patient, at a minimum, should then be followed up for at least 10 weeks from last study treatment administration or up to recovery or stabilization of any AE to be followed-up as specified in this protocol, whichever comes last.

A final End of Study phone call will take place with assessments at 10 weeks after the premature treatment discontinuation.

All definitive discontinuation of study treatment should be recorded by the Investigator in the appropriate screens of the e-CRF and in the patient's medical records when considered as confirmed. IVRS/IWRS should be notified when a patient prematurely discontinues study treatment.

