11.4.4.1 Analyses of quality of life/health economics variables

The analysis of data from EQ-5D instrument will be performed on efficacy population.

Descriptive summaries for individual EQ-5D items.

• Frequency and proportion of patients within each EQ-5D domain and response categories will be summarized by visits on which EQ-5D is assessed (Weeks 0,12, 24, 48, and End of OLETP)

Descriptive summaries for EQ-5D utility scores.

• Response from individual items will be converted into a single EQ-5D utility score by means of a standard regression model. Summary statistics for the utility score (number, mean, median, Q1, Q3, standard deviation, minimum and maximum) will be calculated by visits on which EQ-5D is assessed (Weeks 0, 12, 24, 48, and End of OLETP). Change in mean EQ-5D utility scores from baseline (Week 0) to Weeks 12, 24, 48, and End of OLETP, will be calculated.

Further details will be provided in SAP.

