# 2.4.9 Analyses of quality of life/health economics variables

The analysis of data from EQ-5D instrument will be performed on quality-of-life population, overall as well as separately according to treatment received in the parent study (placebo versus alirocumab (regardless of dose)). Baseline is defined as the baseline of the parent study. Analysis window for efficacy parameters will be used to assign time points (see Section 2.5.4, Table 1).

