#### *EQ-5D utility score*

The raw value and the change from baseline of the utility score will be summarized using mean, median, Q1, Q3, SD, minimum and maximum for each post-baseline visit. Cumulative distribution functions for the change in utility score from baseline will be displayed over time.

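### The SAP's study-day windows give EQ-5D no End-of-OLETP summary: end-of-treatment questionnaires before day 1148 go under other week labels or into no by-visit table

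*SAP*

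**What the plan says.** **Protocol, time points.** Section 9.3.2 lists as an EQ-5D endpoint: "Change in mean EQ-5D utility scores from baseline to Weeks 12, 24, 48, and End of OLETP". It names the same time points for the response categories. Section 11.4.4.1 repeats them in the analysis text: "Change in mean EQ-5D utility scores from baseline (Week 0) to Weeks 12, 24, 48, and End of OLETP". In the flow chart (1.2), the only EQ-5D assessment after Week 48 is at Visit 17, the EOT visit.

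**Protocol, timing of EOT.** Section 6.2.1 gives the study duration as "approximately 168 weeks for the first patients enrolled or until the drug is commercially available for the patient in the respective country". Section 10.1.1.17 adds that "the End-of-treatment visit might be performed earlier than on Week 168 according to the date of inclusion of each patient". Under 10.3.4, patients who stop treatment early "should undergo an unscheduled visit with assessments normally planned at the end of treatment visit". EOT is therefore tied to the end of each patient's treatment, not to a fixed study day.

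**SAP.** Section 2.4.9 says of EQ-5D: "Analysis window for efficacy parameters will be used to assign time points", with a reference to Table 1. Section 2.5.4 confirms the scope: "Data analyzed by time point (including efficacy, laboratory safety data, vital signs, quality of life, ADA) will be summarized using the analysis windows" listed there. Table 1 has 16 rows, Week 4 to Week 168, and none for EOT or End of OLETP. The utility score and its change "will be summarized using mean, median, Q1, Q3, SD, minimum and maximum for each post-baseline visit". Section 1.5 reports only the interim-analysis amendment, and section 1.6 is marked as not applicable.

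**The concern.** A time point that the protocol names separately from the fixed weeks has no matching rule in the SAP. A programmer who follows SAP 2.4.9 and 2.5.4 sorts each EOT questionnaire by study day alone, with four possible results:

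- On days 1148 to 1203 it appears under Week 168.
- In the window of a week with no scheduled EQ-5D (for example Week 60 or Week 108), it forms a small row that the protocol never planned.
- In the Week 12, 24 or 48 window it mixes with scheduled questionnaires. If the patient also has a scheduled one there, the nearest-to-target rule in 2.5.4 keeps a single value, and the EOT value may be the one discarded.
- In a gap between windows, or outside all of them, it enters no by-visit table.

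The quality-of-life population (SAP 2.3.3) carries no window condition, unlike the mITT population (2.3.1). A patient can therefore count in the population and still have a questionnaire that reaches no row.

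At stake is the only EQ-5D information scheduled after Week 48. It would be reported in fragments under week labels, without the end-of-treatment change that the protocol specifies.

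**Working it through.** The plan states no figure for this point, so the check is a day count on SAP Table 1.

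**Inputs.** The 16 windows of Table 1, with Day 1 the first OLE injection. The upper limit of the Week 12 window is the smaller of day 98 and the day of first injection from the Week 12 kit. It is taken at its maximum of 98, which makes the gap total a minimum.

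**Step 1: gaps.** Gap length = (start of next window − 1) − end of previous window.

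| Gap (days) | Length |
|---|---|
| 99–154 | 56 |
| 183–238 | 56 |
| 267–315 | 49 |
| 358–399 | 42 |
| 442–483 | 42 |
| 526–567 | 42 |
| 610–651 | 42 |
| 694–728 | 35 |
| 785–812 | 28 |
| 869–895 | 27 |
| 952–979 | 28 |
| 1036–1063 | 28 |
| 1120–1147 | 28 |

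The sum is 503 days in 13 gaps. Days before 15 and after 1203 also have no window.

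**Step 2: where an EOT day before the Week 168 window lands.** Days 15 to 1147 are 1133 days.

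- In a gap: 503/1133 = 44%.
- In the window of a week with no scheduled EQ-5D (4, 8, 36, 60 to 156): 28 + 28 + 28 + 4×42 + 5×56 = 532; 532/1133 = 47%.
- In the Week 12, 24 or 48 window: 28 + 28 + 42 = 98; 98/1133 = 9%.

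**Step 3: sensitivity to the range of EOT days.** These are shares of calendar days. They would be shares of patients only if EOT days were uniform over the range, which the documents do not say.

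| EOT days | In a gap | Under Week 168 | Under another week |
|---|---|---|---|
| 1148–1203 | 0/56 = 0% | 56/56 = 100% | 0% |
| 980–1203 | 56/224 = 25% | 56/224 = 25% | 112/224 = 50% |
| 813–1203 | 111/391 = 28% | 56/391 = 14% | 224/391 = 57% |
| 99–1203 | 503/1105 = 46% | 56/1105 = 5% | 546/1105 = 49% |

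**Step 4: is uniformity plausible?** Not for completers. A kit holds 6 auto-injectors (Protocol 8.5), injections are every 2 weeks, dispensing is every 12 weeks from Week 24, and completers have EOT 2 weeks after the last injection (6.2.1). A completer who uses a full kit on schedule has the last injection 5×2 = 10 weeks after dispensing and EOT at 10 + 2 = 12 weeks, which is a scheduled visit day. From Week 24 on, each scheduled day ±7 lies inside a Table 1 window (Week 24: 162–176 within 155–182; Week 132: 918–932 within 896–951). These patients would have a gap share of 0% at any such visit, although before Week 168 they would still carry another week's label. Early discontinuers can fall on any day.

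**Step 5: does another SAP rule cover the case?** The last on-treatment value in SAP 2.4.5 is for quantitative safety parameters, not EQ-5D. Section 2.5.5 on unscheduled visits names efficacy, safety laboratory data and vital signs, and is silent on quality of life.

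**Step 6: baseline.** Protocol 11.4.4.1 measures the utility change from Week 0, a visit at which the OLE flow chart schedules EQ-5D. SAP 2.1.9 and 2.4.9 use the parent-study baseline. An added row would need to say which applies.

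**The case against.** The strongest reply is that Week 168 already is the End-of-OLETP row. The protocol summary equates the end of the OLE treatment period with Visit 17, and the flow chart puts Visit 17 in the Week 168/EOT column. This stands for the nominal case, so a reader should not infer that the SAP has no place at all for EOT questionnaires. It does not cover EOT visits before day 1148, which the protocol expressly foresees.

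A second reply is that summaries for each post-baseline visit could include the EOT visit as such. That reading is possible, but 2.4.9 assigns time points by study-day window, not visit label. What can be said is that no pooled summary is specified, not that none could be produced.

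Third, a reader might infer from 2.5.5 that EQ-5D from the early-discontinuation visit is excluded. The text does not support that: 2.5.5 is permissive and excludes nothing, and 2.5.4 applies the windows to quality of life without limiting them to scheduled visits. Its use is simply not stated.

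Fourth, the protocol leaves EQ-5D details to the SAP, the SAP restates the endpoint as change over time (2.1.9), and a pooled row mixes treatment durations. These are fair reasons to keep the by-week rows, and even to drop the pooled one. They do not justify dropping a named time point without recording it.

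**Conclusion.** The point holds as a minor correction. The protocol names End of OLETP as an EQ-5D time point. The SAP's windows place only EOT questionnaires on days 1148 to 1203 under the row that corresponds to it. Earlier ones go under other week labels or, on at least 503 days in 13 gaps between days 99 and 1147, into no by-visit table. The SAP declares no change.

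The number of patients affected cannot be derived. A reader might take the 25% to 46% gap shares as estimates of questionnaires lost. They are day shares under an assumed uniform EOT day. Completers whose EOT falls on a 12-week visit day from Week 24 on would lie inside a window, and if every EOT visit fell on days 1148 to 1203 the gap share would be zero.

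EQ-5D is an other endpoint, analysed descriptively. The primary safety objective and the secondary objectives (lipid efficacy and immunogenicity) are not affected.

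**What to change.** - In SAP 2.4.9 and 2.5.4, add an End-of-OLETP row for the EQ-5D items and the utility score. Use the questionnaire from the EOT visit, or from the early-discontinuation visit with EOT assessments, whatever the study day and with no carry-forward from earlier visits.
- Print N and median treatment duration with the row, because it mixes durations. Keep the by-week rows unchanged.
- State the baseline for the change and reconcile Week 0 (Protocol 11.4.4.1) with the parent-study baseline (SAP 2.1.9 and 2.4.9), for example by showing both where available.
- For clarity, say in SAP 2.5.5 that EQ-5D from the early-discontinuation visit is used.
- If the sponsor intends to drop End of OLETP, record that in SAP 1.6 instead.

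The cost is SAP wording and one extra row per EQ-5D table (or two sets of change figures if both baselines are shown). No new assessments are needed.

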#### 2.5.5 Unscheduled visits

For efficacy, safety laboratory data, or vital signs, unscheduled visit measurements may be used to provide a measurement for a time point, a baseline, a last or a worst value, if appropriate according to their definitions. The measurements may also be used to determine abnormal/PCSA.

# 2.5.6 Pooling of centers for statistical analyses

No pooling of centers will be performed for safety nor for efficacy analyses.

# 3 INTERIM ANALYSIS

Interim analyses may be performed before the end of the study if requested by Health Authorities or if needed for the purpose of scientific communication.

Analyses methods and conventions described in the other sections of this SAP will be applied for all analyses as applicable. The following additional rules will apply for analyses performed at interim analysis:

- Patients without end of treatment visit performed at the time of the cut-off date will be considered as ongoing and exposed up to the cut-off date. Therefore:
  - Patients who did not complete treatment period nor prematurely discontinued the study treatment at cut-off date will be analyzed as "ongoing" in the disposition summary.
  - Their TEAE period, treatment period, efficacy treatment period and on-study observation period will end at the cut-off date.
  - Their treatment duration will be derived by considering date of cut-off as last injection date.
- Analyses of number of injections, mean injection frequency, percentage of days with under/above-planned dosing and compliance will be performed up to the last injection reported in the e-CRF up to the cut-off date.
- AEs occurring, worsening or becoming serious after the cut-off date will not be included in the analyses. However, any available outcome before database lock, regardless of timing in relation to the cut-off date, of an adverse event starting prior to the cut-off date will be taken into account. Medications, treatment discontinuations/completions and deaths occurring after the cut-off date will not be included in the analyses.
- Post-treatment period, post-study period are not applicable for ongoing patients. Analyses
  of post-treatment AEs, post-study deaths and post-treatment medications will be performed
  for patients who either completed or prematurely discontinued the treatment before or at
  the cut-off date.
- Analysis of proportion of patients with insufficient follow-up will be provided for patients
  who either completed or prematurely discontinued the treatment before or at the cut-off
  date.

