10.3.5 Procedure and consequence for patient withdrawal from study

The patients may withdraw from the study before study completion if they decide to do so, at any time and irrespective of the reason. If possible, the patients should be assessed using the procedure defined above.

All study withdrawals should be recorded by the Investigator in the appropriate screens of the e-CRF and in the patient's medical records (with, in this medical records, at least date of withdrawal and reason for) when considered as confirmed.

For patients who fail to return to the site, the Investigator should make the best effort to re-contact the patient (eg, contacting patient's family or private physician, reviewing available registries or health care databases), and to determine his/her health status, including at least his/her vital status. Attempts to contact such patients must be documented in the patient's records (eg, times and dates of attempted telephone contact, receipt for sending a registered letter)

Patients who have withdrawn from the study cannot be included in the study again. Their inclusion and treatment numbers must not be reused.

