### Observation period

The period of safety observation starts from the time when the patient gives informed consent and is divided into the following periods:

- The PRE-TREATMENT period: defined as the time from the signed informed consent date up to the time of first dose of alirocumab in the OLE study. The adverse events occurring during this period were to be reported and recorded in the parent study database. However, after the lock of parent study database, some exceptional pre-treatment adverse events have been recorded in the OLE study database with a start date in the parent study period.
- The treatment-emergent adverse event (TEAE) period: defined as the time from the first dose of alirocumab in the OLE study up to the day of last dose of alirocumab received in the OLE study + 70 days (10 weeks), as residual effect of alirocumab is expected until 10 weeks after the stop of alirocumab.

The TEAE period will include:

- The TREATMENT period defined as the time from the first dose of alirocumab in the OLE study up to the day of last dose of alirocumab received in the OLE study + 21 days.
- The POST-TREATMENT period: defined as the time starting the day after the end of TEAE period up to the end of study

The on-study observation period is defined as the time from first dose of alirocumab in the OLE study until the last protocol planned visit of the patient in the OLE study. The last protocol planned visit is defined as the safety follow-up call if done, else 10 weeks after last injection of alirocumab.

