#### 2.1.4.2 Deaths

The deaths observation period are per the observation periods defined above.

- Death on-study: deaths occurring during the on-study observation period
- Death on-treatment: deaths occurring during the treatment-emergent adverse event period
- Death post-study: deaths occurring after the last planned protocol visit

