#### Analysis of all treatment-emergent adverse events

The following TEAE summaries will be generated:

- Overview of TEAEs, summarizing number (%) of patients with any
  - TEAE;
  - Serious TEAE;
  - TEAE leading to death;
  - TEAE leading to permanent treatment discontinuation.
- All TEAEs by primary SOC, HLGT, HLT, and PT
- Number (%) of patients experiencing common TEAE(s) presented by primary SOC, HLT and PT (HLT incidence ≥2 % in overall patients in the OLE), sorted by SOC internationally agreed order and by alphabetic order for the other levels (HLT and PT);
- All TEAEs by primary SOC and PT, sorted by the internationally agreed SOC order and by decreasing incidence of PTs within each SOC. This sorting order will be applied to all other tables by SOC and PT of TEAEs, unless otherwise specified;
- All TEAEs regardless of relationship in one column and, in the same table a second column with TEAEs related to alirocumab according to investigator's opinion by primary SOC, HLGT, HLT and PT;
- All TEAEs by maximal intensity (ie, mild, moderate or severe), presented by primary SOC and PT, sorted by the sorting order defined above;
- The event rate per patient-year (the number of patients with an event in question divided by total patient-years in OLE study) will be provided for all TEAEs by SOC and PT. For a patient with event, patient year is censored at time of first event in OLE; for patient without event, it corresponds to length of OLE TEAE period;
- Kaplan-Meier curves will be provided, when appropriate, for time from first dose of OLE study treatment to the first occurrence of selected TEAEs as well as incidence rates at 24, 52, 78, 104 and 156 weeks of exposure. Patients without any event will be censored at the end of the TEAE period. Selected TEAEs could be local injection site reactions, general allergic reactions, hepatic disorders, diabetes among non-diabetic patients at baseline, and TEAE related to any clinically significant signal that needs further characterization.

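### Interim only: SAP Section 3 decides who is still exposed by a missing EOT visit, not by treatment status, so patients who stopped without that visit can be run on to the cut-off

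*SAP*

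**What the plan says.** SAP Section 3 (Interim analysis) adds rules for patients whose follow-up is incomplete at the cut-off.

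- **Opening rule, which runs exposure to the cut-off:** "Patients without end of treatment visit performed at the time of the cut-off date will be considered as ongoing and exposed".
- **First sub-bullet, which sets the disposition label of ongoing:** "Patients who did not complete treatment period nor prematurely discontinued the study treatment at cut-off date will be analyzed as".
- **Next sub-bullets:** 'their' TEAE, treatment, efficacy and on-study periods stop at the cut-off, and the cut-off stands in for the last injection date when treatment duration is computed.
- **Later bullets:** "Post-treatment period, post-study period are not applicable for ongoing patients". Post-treatment AEs, post-study deaths and adequacy of follow-up are analysed in patients who completed or prematurely discontinued by the cut-off.

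Elsewhere the SAP ties these periods to the actual last dose: +70 days for the TEAE period and +21 days for the treatment period (2.1.4), and +21 days for the efficacy period (2.3.1). For patient-year rates (2.4.5.1) the denominator rule is "for patient without event, it corresponds to length of OLE TEAE period". SAP 2.1.4.2 has "Death on-treatment: deaths occurring during the treatment-emergent adverse event period".

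Protocol 10.3.5 foresees patients who do not come back. It makes the closing assessment of a withdrawn patient conditional on feasibility, and asks sites to "determine his/her health status, including at least his/her vital status".

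**The concern.** The opening rule and the first sub-bullet do not select the same patients. A patient with a recorded discontinuation, a withdrawal or a known death, but no EOT visit, is ongoing under the first and not under the second. 'Their' in the period rules can refer to either group.

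Under the opening rule these patients contribute at-risk time when they were off drug, out of contact or dead. That time dilutes TEAE rates per patient-year and moves TEAE Kaplan-Meier censoring to the cut-off. It also moves the boundary for on-treatment death. The interim was added for Health Authority requests and scientific communication (SAP 1.5), and safety is the primary objective, so the choice should be settled before any cut-off.

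**Working it through.** The plan states no figure on this point: no cut-off date, no expected number without an EOT visit and no event rate. The check is therefore a comparison of rules followed by date arithmetic.

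**1. Rules side by side, for a patient who permanently stopped without an EOT visit**

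| Item | Opening rule of Section 3 | Sub-bullet status with SAP 2.1.4 |
|---|---|---|
| Status | Ongoing | Discontinued |
| TEAE period ends | Cut-off | Earlier of cut-off and last dose +70 days |
| Death after day 70, no follow-up call | On-treatment | Post-study |

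The last row follows because, without a follow-up call, SAP 2.1.4 ends the on-study period 10 weeks after the last injection.

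**2. Excess per patient.** Let gap = cut-off minus last injection, in days. Excess TEAE time = max(0, gap − 70).

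- 12 weeks: 84 − 70 = 14 days
- 24 weeks: 168 − 70 = 98 days
- 48 weeks: 336 − 70 = 266 days

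**3. Mean excess.** Assume stops are spread evenly over Day 1 to cut-off day C. The mean of max(0, C − L − 70), with L the day of the last injection, is (C − 71)(C − 70)/(2C).

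- C = 337: 266 × 267/674 = 105.4 days
- C = 505: 434 × 435/1,010 = 186.9 days
- C = 673: 602 × 603/1,346 = 269.7 days

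These are the protocol's nominal days for Weeks 48, 72 and 96; using them as interim follow-up is an assumption. Averaged over staggered follow-up from 337 to 673 days, the mean excess is 187.1 days, and 187.1/365.25 = 0.512 patient-years.

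**4. Study level.** With 1,200 patients (the planned maximum) and mean follow-up of 505 days, total TEAE time is 1,200 × 505/365.25 = 1,659 patient-years.

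- 1% affected (12 patients, assumed): 12 × 0.512 = 6.1 patient-years; 6.1/1,659 = 0.37%
- 3% affected (36 patients, assumed): 36 × 0.512 = 18.4 patient-years; 18.4/1,659 = 1.11%

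**5. A harsher case.** Suppose all affected patients had their last injection at Week 24 and the cut-off is Week 96 for everyone. Each gains 96 − 34 = 62 weeks. TEAE time becomes 2,208 patient-years instead of 2,194 (1% affected) or 2,165 (3% affected), an overstatement of 0.65% or 1.98%.

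Steps 4 and 5 are ceilings for any single event type, because SAP 2.4.5.1 stops a patient's time at the first event.

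**6. One death moved to on-treatment:** 1/1,200 = 0.083 percentage points.

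**The case against.** The strongest reply is that Section 3 largely resolves itself. The opening rule leads into a sub-bullet based on treatment status, which is the nearest antecedent of 'their'. Later bullets use the same status, and the SAP's other conventions apply where applicable. On that reading a recorded discontinuation keeps its last dose +70 days, and post-study deaths in such patients are analysed as such. This reading is available, and under it the death example disappears. It is not the only reading, however: the opening rule is an explicit instruction that says something else.

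Four stronger readings are tempting but not supported.

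- **That Protocol 10.3.4 makes the EOT visit optional.** Its wording, "it should take place within 5 days of treatment discontinuation, if possible", most naturally qualifies the 5-day timing; the visit itself is one that patients should undergo. Section 10.3.5 is the better evidence that some patients will have no EOT visit.
- **That patients with an open temporary interruption are miscounted.** SAP 2.4.3.1 measures exposure regardless of intermittent discontinuations, and a patient who may resume has no established last dose.
- **That efficacy results are distorted.** Efficacy summaries use observed values without imputation (SAP 2.4.4.2), so a patient who no longer attends adds none. Laboratory and vital-sign Kaplan-Meier analyses censor at the last assessment and are also untouched.
- **That ending periods at the cut-off is wrong in general.** It is sensible for patients still dosing, whose injection data arrive at visits up to 12 weeks apart.

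**Conclusion.** The concern stands as a small, interim-only defect of wording. Followed literally, the opening rule of SAP Section 3 assigns at-risk time in conflict with SAP 2.1.4 and with the status test in the same section.

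The overall effect is about 0.4% to 1.1% of TEAE time. This assumes that 1% to 3% of 1,200 patients are affected, with stops spread evenly and follow-up of 337 to 673 days. It reaches about 2% in the harsher case above. Overall rates barely move.

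Counts of rare outcomes are more sensitive. A late death could be labelled on-treatment, but only under the literal reading. A reader might infer that interim safety rates would be materially biased, or that the final report is affected. The documents support neither: the size is small under the assumed rates, and the final-analysis periods run from the last dose.

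**What to change.** Replace the opening rule of SAP Section 3 with wording such as:

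> A patient is ongoing, and exposed to the cut-off, if no treatment completion, permanent treatment discontinuation, study withdrawal or death is recorded on or before the cut-off date. For every other patient, whether or not an EOT visit took place, the actual last injection date is used (imputed under Section 2.5.3 if missing, for the analysis periods). The TEAE, treatment and efficacy periods of these patients end at the earlier of the cut-off date and last injection +70, +21 and +21 days respectively.

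The sub-bullets that follow then apply to ongoing patients only. No extra disposition line or sensitivity summary is needed for open interruptions.

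One limit should be stated. Discontinuation and withdrawal are entered in the e-CRF once considered confirmed (Protocol 10.3.4 and 10.3.5), so a patient who has stopped with nothing yet recorded remains ongoing under this rule.

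The cost is one SAP rule, using status and dates the e-CRF already holds. There is no protocol amendment, no new data collection, and no change for patients still dosing or for the final analysis.
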